### **6.1.3. Clinical Rationale for CUDC-907 Use in RR MYC-Altered DLBCL**

The utility of HDAC and PI3K inhibitors for the treatment of hematological malignancies has been recognized by the U.S. FDA, which has approved 4 HDAC inhibitors and 1 PI3K inhibitor for various hematological cancer indications.

The therapeutic potential of CUDC-907 is shown by safety and efficacy data from the completed dose escalation and ongoing expansion stages of ongoing study CUDC-907-101, the first-in-human (FIH) trial. CUDC-907-101 is a Phase 1, open-label, multicenter, dose-escalation trial to evaluate the safety and tolerability of CUDC-907 as a single agent administered orally to subjects with RR lymphoma or multiple myeloma (MM). In the completed dose-escalation phase of CUDC-907-101, subjects received CUDC-907 capsules orally, within 30 minutes of meals, in 21-day cycles according to one of three dosing schedules: once daily (QD), intermittent twice (BIW) or thrice weekly (TIW), and five days on/two days off (5/2). Objective responses, in some cases of extended duration, were achieved with CUDC-907 monotherapy on all schedules tested. On the basis of improved tolerability and comparable efficacy, CUDC-907 administered at 60 mg on the 5/2 schedule was determined to be the recommended Phase 2 dose (RP2D).

CUDC-907 monotherapy has demonstrated a manageable side effect profile and achieved objective responses (ORs) as well as sustained disease control, particularly in the setting of RR DLBCL. The most common treatment-related AEs of any grade have been diarrhea, fatigue, thrombocytopenia, and nausea. No dose-limiting toxicities (DLTs) were observed on the 60 mg 5/2 schedule.

As of the 15 March 2016 data cut-off, among 21 response-evaluable subjects with RR DLBCL receiving CUDC-907 monotherapy at the 60 mg 5/2 schedule (n = 18), or in combination with rituximab (n = 3), 9 (43%) achieved objective responses (3 CRs and 6 partial responses [PRs]); lasting a median of 2.6 months (range: < 1-14+). Among the 5 response-evaluable subjects with MYC-altered DLBCL, 4 (80%) achieved objective responses (3 CRs and 1 PR). Three of these response-evaluable subjects were found to overexpress MYC ( $\geq 40\%$ ) and BCL2 ( $\geq 70\%$ ) by IHC, meeting criteria applied to “double-expressor” (DE) DLBCL. Two of the DE subjects attained objective responses: 1 CR (followed by autologous stem cell transplant) and 1 PR (lasting 4 months). The third subject has experienced lengthy disease stabilization (5.7+ months). All 3 CRs observed on this study occurred in subjects with MYC gene copy number gain, including the subject who also had DE DLBCL. Durable clinical benefit in subjects with RR MYC-altered DLBCL in FIH testing further supports this Phase 2 study of CUDC-907.

## 6.2. Justification of Study Design Considerations

The following is a brief summary of key study design considerations:

- Study subjects will be  $\geq 18$  years of age with histopathologically confirmed diagnosis of RR DLBCL (including t-FL/DLBCL) who have received at least 2 but no more than 4 prior lines of treatment for DLBCL, and ineligible for (or failed) autologous or allogeneic SCT.
- Subjects will receive CUDC-907 60 mg administered orally on a 5/2 schedule until progression of disease or other criteria for discontinuation of treatment. Each cycle will consist of 21 days.

## 6.3. Potential Risk and Benefits

Based on available preclinical and clinical safety and response data emerging from the ongoing CUDC-907-101 and CUDC-907-102 trials, ongoing clinical testing of CUDC-907 is considered justified using the dose and dosage regimen preliminarily shown to be reasonably safe and tolerable (Sections 6.1.2, **Error! Reference source not found.** and 6.1.3).

### 6.3.1. Potential Risks

In CUDC-907-101, low grade (Grade 1 and 2) diarrhea, fatigue, and nausea were the most common drug-related adverse events (AEs) reported in the study. A total of 4 DLTs consisting of diarrhea and hyperglycemia occurred in 3 subjects treated at the highest doses on the QD (60 mg) and intermittent schedules (150 mg BIW and 150 mg TIW). Other drug-related Grade 3 or 4 AEs reported in 2 or more subjects included thrombocytopenia and neutropenia (hematologic AEs) as well as diarrhea, hyperglycemia, and fatigue (non-hematologic AEs). As a result, stringent monitoring of blood counts will be performed.

The planned CUDC-907 dose level, 60 mg 5/2, was reasonably tolerated in the dose-escalation phase of CUDC-907-101 and is currently undergoing further examination in the expansion phase of the trial in subjects with RR DLBCL.

### 6.3.2. Potential Benefits

Preliminary antitumor efficacy data from CUDC-907-101 evaluating CUDC-907 as monotherapy in subjects with RR DLBCL, including subjects with DE disease, have been promising.

## 6.4. Good Clinical Practice Statement

The study will be conducted in accordance with ethical principles that have their origin in the Declaration of Helsinki and are consistent with International Conference on Harmonisation, Good Clinical Practice (GCP) guidelines, applicable regulatory requirements, and Curis policies.

## **7. TRIAL OBJECTIVES**

### **7.1. Primary Objective**

- To evaluate the efficacy of CUDC-907 as measured by the objective response rate (ORR) in subjects with RR DLBCL with MYC-altered disease.

### **7.2. Secondary Objectives**

- To evaluate PFS, median PFS, and PFS at 6 months (PFS6).
- To evaluate OS.
- To evaluate the disease control rate (DCR) and duration of response (DOR).
- To evaluate the incidence and severity of AEs, serious adverse events (SAEs), and other safety parameters in subjects receiving CUDC-907.
- To characterize the pharmacokinetics (PK) of CUDC-907.

### **7.3. Exploratory Objectives**

- To explore the effects of CUDC-907 on disease-associated biomarkers.
- To explore the relationship between disease-associated biomarkers in plasma and tumor tissue. Among biomarkers of interest, BCL2 and BCL6 protein expression and translocation status in particular will be tested in tumor tissue, where possible.
- To explore biomarkers of response for patient selection.
- To explore the relationship between additional biomarkers and biomarker profiles that may influence biologic and clinical responses to CUDC-907.
- To explore the ORR according to Lugano classification ([Cheson et al, 2014](#); [Barrington et al, 2014](#)).

## 8. STUDY DESIGN

### 8.1. Overall Study Design

This is a Phase 2, open-label, multicenter trial designed to evaluate the efficacy and safety of CUDC-907 in subjects 18 years and older with RR MYC-altered DLBCL.

[Figure 1](#) depicts the study design. Patients with RR DLBCL will be eligible for treatment with CUDC-907 as long as they have tumor tissue available that can be tested for MYC-altered disease. This is defined as *MYC* translocation by FISH, or *MYC* expression in  $\geq 40\%$  of tumor cells by IHC staining, and/or *MYC* gene copy number gain by FISH based on central testing of one of the following:

- Fresh tumor tissue obtained from biopsy accessible lesions with low estimated risk for serious complications (less than 2%), or
- Archived tumor tissue (most recent available)

Subjects will be required to submit archival tumor samples (most recent available) or fresh tumor samples for central FISH and IHC testing. Subjects whose tumors have been previously characterized as MYC-altered are strongly encouraged to enter the study. For subjects who enter the study with unconfirmed MYC-altered disease, fresh tumor samples are preferred.

All eligible subjects will receive the following treatment:

- CUDC-907 60 mg ( $2 \times 30$  mg capsules) orally (PO) for 5 days on/2 days off (5/2) (21-day cycles).

Based on central testing and review, subjects will be classified into one of the following categories:

- (1) Group A: *MYC* translocation+ by FISH,
- (2) Group B: *MYC* expression in  $\geq 40\%$  of tumor cells by IHC and/or *MYC* gene copy number gain by FISH, or
- (3) Group C: *MYC* translocation by FISH, and *MYC* expression in  $< 40\%$  of tumor cells, and no *MYC* gene copy number gain by FISH.

Subjects will be assigned to Groups A, B, or C according to their *MYC* status as described above. Subjects who are both *MYC* translocation+ by FISH and have *MYC* expression in  $\geq 40\%$  of tumor cells by IHC and/or *MYC* gene copy number gain by FISH will be classified as *MYC* translocation+ and assigned to Group A. Enrollment may continue until the minimum number of subjects are enrolled in Groups A and B.

Subjects in all groups will continue to receive treatment until they meet criteria for treatment discontinuation.

Efficacy evaluations will include restaging assessments, physical examination, review of lymphoma symptoms, survival status, and other procedures, as necessary. Disease response by radiologic imaging will be assessed according to the Revised Response Criteria for Malignant Lymphoma ([Cheson et al, 2007](#)). The exploratory efficacy endpoint of ORR will be assessed according to Lugano classification ([Cheson et al, 2014](#); [Barrington et al, 2014](#)).

Efficacy assessments will be performed using computed tomography/magnetic resonance imaging (CT/MRI) scans of the neck, chest, abdomen, and pelvis.

Skull base-to-mid thigh PET scan is recommended but not mandated. Contrast-enhanced MRI may be used to evaluate sites of disease that cannot be adequately imaged using CT or if contrast-enhanced CT scanning cannot be performed due to medical condition(s). For each subject, the modality/modalities utilized at screening will be followed throughout the subject's time on study. While additional modalities may be used depending on assessment needs and disease specifics, technologies used at screening will continue to be followed at each restaging assessment to enable direct comparison with the baseline assessment.

Subjects will have efficacy assessments (CT/MRI) performed at the end of Cycles 2, 4, and 6 (each  $\pm$  3 days). If FDG-PET/CT is acquired at baseline, follow-up FDG-PET/CT imaging at Cycle 4 and at Cycle 10 is required. Scans will be sent for a central radiographic review. Subjects who continue to receive CUDC-907 after Cycle 6 will have a disease assessment (CT/MRI) performed every 12 weeks  $\pm$  1 week (i.e., Cycles 10, 14, 18) until Cycle 18 in the first 12 months with scans collected through the first year, then every 24 weeks  $\pm$  2 weeks (i.e., Cycles 26, 34) until PD or death, or up to 2 years, whichever occurs first. After that, disease assessments may be performed as clinically indicated (i.e., at the discretion of the Investigator or per standard of care).

Safety will be assessed by the incidence and severity of AEs as determined by National Cancer Institute Common Terminology Criteria for Adverse Events (NCI CTCAE v4.03). Additional safety parameters will include physical examination and vital signs, as well as hematology and serum chemistry laboratory tests ([Section 11.2](#)).

## **8.2. Number of Subjects**

Approximately 200 subjects will be enrolled in the study.

## **8.3. Dose and Schedule**

### **8.3.1. Dose and Mode of Administration**

Subjects will receive:

- CUDC-907 60 mg (2  $\times$  30 mg capsules) orally (PO) for 5 days on/2 days off (5/2) (21-day cycles)

CUDC-907 will be administered PO with meals ( $\pm$  30 minutes). CUDC-907 will be administered in the clinic on days of PK blood sampling, biopsy sampling, and on Day 1 of each cycle up to Cycle 13. Beginning on Cycle 14, in-clinic dosing will only be required on Day 1 of even numbered cycles (i.e., Cycles 14, 16, 18, etc.).

If a dose is missed or vomited, the subject will be instructed to skip that dose and report it to the Principal Investigator (PI) as soon as possible. Missed or vomited doses should not be made up.

Subjects must meet retreatment criteria in order to continue receiving study treatment (see [Section 10.5.2](#)).

Treatment delays and dose reductions will be allowed as specified in Section 10.5.3; however subjects who experience a Grade 4 DLT-like event must be discontinued from further study treatment.

For full study treatment details, see Section 10.

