### 10.5.3. Safety Criteria for Adjustment or Stopping CUDC-907

#### 10.5.3.1. Dose Delays and Discontinuation of CUDC-907

In the event that any of the above criteria are not met, study drug dosing must be held until the retreatment criteria are met. Treatment may then resume at the full dose of CUDC-907, as long as none of the criteria in Table 2 are met. Beyond Cycle 1, subjects held for  $> 7$  days may restart treatment after the subject has met the above criteria and following discussion and agreement between the Investigator and the Medical Monitor. Beyond Cycle 2, subjects may have study drug held for up to 7 days between the end of a cycle and initiation of another (e.g., Cycle 2 Day 21 to Cycle 3 Day 1). This hold will be at the discretion of the Investigator and after discussion and agreement between the Investigator and Medical Monitor.

Study treatment should be discontinued in the event of an unacceptable toxicity or treatment hold lasting more than 4 weeks, except in cases of clinical benefit determined by the Investigator with approval by the Sponsor Medical Monitor.

Subjects who experience a DLT-like event will be either discontinued from further study treatment or their dose will be reduced following discussion and agreement between the Investigator and the Sponsor's Medical Monitor. A DLT-like event will be defined as any of the following AEs occurring at any time:

- Non-hematological  $\geq$  Grade 3 AE, other than Grade 3 nausea or Grade 3 vomiting in subjects treated with less than optimal antiemetic therapy.
- An AE resulting in a dose delay of  $\geq$  7 consecutive days (e.g., 6 consecutive missed doses).
- Grade 4 neutropenia  $\geq$  7 days, or  $\geq$  Grade 3 neutropenia with fever  $>$  101.3°F (38.5°C) or  $\geq$  Grade 3 neutropenia with infection.
- Grade 4 thrombocytopenia  $\geq$  7 days, or  $\geq$  Grade 3 thrombocytopenia and significant bleeding.

**NOTE:** A DLT-like event excludes AEs that are clearly and incontrovertibly related to the underlying disease or extraneous factors.

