### 10.5.3.3. Dose Adjustments for CUDC-907 Hematologic and Non-hematologic Toxicity

The administration of HDAC and PI3K inhibitors has been associated with predictable bone marrow suppression that is typically transient and reversible.

The administration of HDAC and PI3K inhibitors has also been associated with hyperglycemia. This hyperglycemia does not generally result in severe metabolic complications and typically resolves with therapeutic intervention. The treatment goal for glycemic control is fasting plasma glucose  $<$  160 mg/dL; while making every attempt to avoid hypoglycemia. Dose modifications of CUDC-907 are based on the severity of toxicities.

CUDC-907 dose adjustments for hematologic and non-hematologic toxicities are shown in [Table 2](#).

Table 2: CUDC-907 Dose Adjustments for Hematologic and Non-Hematologic Toxicities			
Thrombocytopenia	Grade 1 or 2 No change in dose	Grade 3 or 4 (platelets < 50,000/μL) Hold treatment until platelets ≥ 50,000/μL or baseline, then reduce dose to the next lower dose level (as applicable per Table 1 ).	Grade 4 thrombocytopenia requiring platelet transfusion Hold treatment until platelets ≥ 75,000/μL or baseline, then dose reduce to the next lower dose level (as applicable per Table 1 ).
Neutropenia	Grade 1 or 2 No change in dose	Grade 3 or 4 (ANC < 1,000/uL) Hold treatment until ANC ≥ 1000/μL, then reduce dose to the next lower dose level (as applicable per Table 1 ).	Grade 4 febrile (≥ 38.5° C) neutropenia Hold treatment until febrile neutropenia resolves and ANC ≥ 1000/μL or baseline, then dose reduce to the next lower dose level (as applicable per Table 1 ).
Anemia	Grade 1 or 2 No change in dose	Grade 3 or 4 (hemoglobin < 8 g/dL) Hold treatment until hemoglobin ≥ 10 g/dL or baseline then reduce dose to the next lower dose level (as applicable per Table 1 ).	Grade 4 anemia requiring transfusion Hold treatment until hemoglobin ≥ 10 g/dL or baseline, then dose reduce to the next lower dose level (as applicable per Table 1 ).
Recurrence of Grade 3 or 4 hematologic toxicity will be cause for a second dose modification. If the starting dose does not permit dose modification, then study drug will be discontinued.			

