**Table 2: CUDC-907 Dose Adjustments for Hematologic and Non-Hematologic Toxicities (Continued)**

Toxicity	Management		
Hyperglycemia	Grade 1/2 or Grade 3 (> 250 – 500 mg/dL) asymptomatic No change in dose 	Grade 3 (> 250 – 500 mg/dL) symptomatic or Grade 4 (> 500 mg/dL) Hold treatment until glucose < 250 mg/dL and asymptomatic; Reduce dose to the next lower dose level (as applicable per Table 1 ).	≥ Grade 3 hyperglycemia not improving despite appropriate treatment for 1 week or symptomatic Grade 4 hyperglycemia (> 500 mg/dL) Hold treatment until glucose < 250 mg/dL and asymptomatic; Reduce dose to the next lower dose level (as applicable per Table 1 ) upon return to ≤ Grade 1 or baseline.

Recurrence of Grade 3 or 4 hyperglycemia will be cause for a second dose modification.  If the starting dose does not permit dose modification, then study drug will be discontinued.  Recurrence of Grade 3 or 4 hyperglycemia that does not recover to ≤ Grade 1 or baseline within 3 weeks after second modification (as applicable) will be grounds for discontinuation of study drug.
			

AEs = adverse events; ANC = absolute neutrophil count

 Transient Grade 1 or 2 hyperglycemia should be monitored per Investigator discretion and medical guidelines.

 An exception for ongoing treatment may be made in the case of Investigator-determined clinical benefit with approval from the Medical Monitor.

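### Section 8.3.1 stops treatment after a Grade 4 DLT-like event, while Table 2 re-doses at a reduced level after Grade 4 febrile neutropenia or Grade 4 hyperglycemia; separately, the QTcF change rule uses a baseline that is never collected

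*Combined protocol and SAP*

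**What the plan says.** Section 8.3.1 refers to Section 10.5.3 for delays and reductions and then makes one exception: "however subjects who experience a Grade 4 DLT-like event must be discontinued from further study treatment". It gives no waiver, and it later refers the reader to Section 10 for full treatment details.

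Section 10.5.3.1 states: "Subjects who experience a DLT-like event will be either discontinued from further study treatment or their dose will be reduced", by agreement between the Investigator and the Medical Monitor. It does not separate Grade 4 from Grade 3. Its definition ("A DLT-like event will be defined as any of the following AEs occurring at any time") covers:
- non-hematological events of Grade 3 or higher, with a nausea and vomiting exception;
- an event causing a dose delay of at least 7 days;
- Grade 4 neutropenia or thrombocytopenia lasting at least 7 days;
- neutropenia of Grade 3 or higher with fever above 38.5 °C or with infection;
- thrombocytopenia of Grade 3 or higher with significant bleeding.

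Events clearly caused by the disease or by extraneous factors are excluded. For unacceptable toxicity the same section says to stop, "except in cases of clinical benefit determined by the Investigator with approval by the Sponsor Medical Monitor".

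In Table 2 (Section 10.5.3.3) the Grade 4 febrile neutropenia cell begins "Hold treatment until febrile neutropenia resolves and ANC" and ends in a dose reduction. Both cells that cover Grade 4 hyperglycemia hold until glucose is below 250 mg/dL "and asymptomatic; Reduce dose to the next lower dose level". The row for other non-hematological events says to discontinue at Grade 4, and footnote 2 permits continued treatment for clinical benefit with Medical Monitor approval.

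Section 11.2.9 sets single ECGs at Screening and End of Therapy (EOT). Its on-treatment QTcF rule uses triplicate ECGs and two limbs: a mean of 480 msec or more, or a rise of more than 60 msec from the pretreatment Cycle 1 Day 1 mean.

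**The concern.** Section 8.3.1 states its Grade 4 rule as an exception to Section 10.5.3, so the two are meant to be read together. A site that opens Table 2 after Grade 4 febrile neutropenia or Grade 4 hyperglycemia finds an order to re-dose a subject whom Section 8.3.1 removes from treatment. At stake is who receives more drug after a Grade 4 toxicity, and whether sites act alike. The choice also decides whether the event is counted among those that led to treatment discontinuation, which the Synopsis lists as a safety measure.

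The ECG problem is of a different kind. A rule that can end treatment depends on a baseline the protocol does not collect and on triplicate recordings it does not schedule.

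**Working it through.** No formula applies and the plan gives no figure to reproduce. The check sets the texts side by side.

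**Grade 4.** Section 8.3.1 applies when an event is both Grade 4 and DLT-like. For each Table 2 entry that covers Grade 4:

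| Table 2 entry | Action | When Section 8.3.1 would require stopping |
|---|---|---|
| Febrile neutropenia, Grade 4 (1 cell) | Hold, then reduce | Fever above 38.5 °C; the cell itself starts at 38.5 °C, so a reading of exactly 38.5 °C falls outside the fever criterion |
| Hyperglycemia (2 cells, which also cover some Grade 3 events) | Hold, then reduce | Grade 4 and recorded as an adverse event |
| Neutropenia, Grade 3 or 4 (1 cell) | Hold, then reduce | Grade 4 that lasts 7 days or more, comes with infection, or delays dosing 7 days or more |
| Thrombocytopenia (2 cells, one of them "Grade 4 thrombocytopenia requiring platelet transfusion") | Hold, then reduce | Grade 4 that lasts 7 days or more, comes with significant bleeding, or delays dosing 7 days or more |
| Anemia (2 cells; hemoglobin back to "10 g/dL or baseline, then dose reduce to the next lower dose level") | Hold, then reduce | Grade 4 that delays dosing 7 days or more |
| Other non-hematological, Grade 4 | Discontinue, subject to footnote 2 | Agrees, apart from the waiver |

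Hyperglycemia is recorded as an adverse event under Section 12.1 if the Investigator judges it clinically significant and it led to an action such as a dose hold. Table 2 itself orders the hold at Grade 4, so only the clinical judgment remains open.

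Cells that hold and then reduce and that cover Grade 4: 1 + 2 + 1 + 2 + 2 = 8. Those that conflict with little more than the cell's own description: 1 + 2 = 3. Those that need a further condition: 1 + 2 + 2 = 5. All 8 fall away if the event is clearly due to disease or extraneous factors. The two recurrence lines, for hematologic toxicity and for hyperglycemia, pool Grades 3 and 4 and call for a second dose modification without excepting Grade 4 DLT-like events.

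Section 9.3.1 does not settle the matter. It sends unmanageable toxicity to Section 10.5.2, which contains only retreatment criteria.

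**Grade 3.** For a Grade 3 non-hematological DLT-like event, Section 10.5.3.1 requires reduction or discontinuation. Table 2 holds treatment and requires a reduction only if recovery takes more than 3 weeks. A subject who recovers within 3 weeks therefore returns at full dose under Table 2 but not under Section 10.5.3.1.

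**QTcF.** In the Schedule of Events (Section 5.1) the ECG row is marked at Days -7 to -1, in 0 of 7 treatment-period columns (Cycle 1 Days 1, 5, 8, 12 and 15; Cycles 2-6; Cycle 7+), and at EOT. The Cycle 1 Day 1 list in Section 13.2.1.1 contains no ECG. The EOT visit falls 30 - 7 = 23 to 30 + 7 = 37 days after the last dose.
- Limb of more than 60 msec: cannot be computed as defined, because its baseline is not collected.
- Limb of 480 msec or more: needs no baseline, but works only on ECGs done outside the schedule.

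**The case against.** The best defense is that Section 10 shows a deliberate intent. Section 10.5.3.3 describes marrow suppression as usually transient and reversible, and says hyperglycemia generally resolves with treatment. Table 2 gives hyperglycemia its own row. Section 8.3.1 refers to Section 10 for details, so one stray sentence could be amended. This stands as an argument about which rule to keep. It does not make the sentence in 8.3.1 any less mandatory.

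There are also safeguards: dosing waits for the retreatment criteria, the Medical Monitor must agree on DLT-like events, and the Safety Review Committee (SRC) reviews toxicity. They limit harm without saying which text governs.

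A reader might infer more than the documents support:
- *That Table 2 never stops treatment at Grade 4.* It does, for non-hematological events other than hyperglycemia.
- *That Section 10.5.3.1 contradicts 8.3.1.* It can be read as a general choice that 8.3.1 narrows at Grade 4. The fault is that it does not repeat the Grade 4 rule.
- *That the SRC stopping guidelines are compromised.* Discontinuation and dose reduction are separate SRC inputs, but none of the three guidelines in Section 9.3.2 depends on which one occurred.
- *That earlier data show these Grade 4 events to be common.* Section 6.3.1 pools Grades 3 and 4 across schedules, and Section 6.1.3 reports no DLTs at 60 mg on the 5/2 schedule.
- *That the QTcF rule is wholly unusable.* The 480 msec limb can be applied to an unscheduled triplicate, and the references to a schedule above can reasonably mean the repeat-ECG steps just before them.

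**Conclusion.** The inconsistency is real and should be fixed. For Grade 4 febrile neutropenia with fever above 38.5 °C, and for Grade 4 hyperglycemia recorded as an adverse event, Section 8.3.1 and Table 2 give opposite orders unless disease or extraneous factors clearly explain the event. The remaining hematologic Grade 4 cells conflict only in the circumstances tabulated above. The footnote 2 waiver and the Grade 3 mismatch are further, smaller differences. The QTcF gap is separate: one limb lacks its baseline, and neither has a scheduled on-treatment measurement.

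The count of 3 and 5 cells is a reading of the text, not a frequency. The documents give no basis for estimating how many subjects would be affected. Nothing here changes the sample size, the ORR confidence intervals or the SRC stopping guidelines.

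**What to change.** 1. **One Grade 4 rule.** By default keep the more protective rule of Section 8.3.1. Repeat it in Section 10.5.3.1, and in the Table 2 cells and recurrence lines that cover Grade 4 events insert *discontinue if the event is Grade 4 and DLT-like; otherwise* before the existing action. If hold-and-reduce is what the clinical team wants, for which Section 10.5.3.3 already offers a rationale, amend the single sentence in 8.3.1 to defer to Table 2. Either way, state whether footnote 2 applies to Grade 4 DLT-like events.
2. **Grade 3.** Align the Table 2 cell for Grade 3 non-hematological events with Section 10.5.3.1.
3. **QTcF.** In Section 11.2.9 define the baseline as the screening ECG already collected (the mean where repeated), say that the on-treatment rule applies to any clinically indicated ECG, and replace the references to a schedule above with the repeat-ECG procedure. This makes the rule computable but adds no on-treatment monitoring. If routine monitoring is intended, the ECGs must go into the Schedule of Events.

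The cost is wording and site notification, with no added visits or ECGs under the default. Keeping the stop rule may discontinue some subjects whom Table 2 would have kept on a lower dose (number unknown), and a single screening ECG is a noisier baseline than a triplicate mean.
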